1 PROTOCOL SUMMARY

1.1 SYNOPSIS

Title:	A futility trial of sirolimus in multiple system atrophy (MSA)
Study Description:	Single-center, randomized, placebo-controlled, phase-II, futility clinical trial to determine if oral sirolimus is of sufficient promise to slow disease progression in MSA, prior to embarking on a large-scale and costly phase III study to assess its efficacy. A futility design under the null hypothesis assumes that sirolimus will slow the progression of the disease, whereas the alternative hypothesis assumes no benefit of sirolimus. If the null hypothesis is rejected (i.e., futility of sirolimus to slow progression of MSA), a major phase III study will be discouraged, whereas non-futility will offer strong support for a phase III trial to detect clinical efficacy.
Objectives:	
Primary objective: To determine if oral sirolimus is of sufficient promise or futile to slow disease progression in MSA.
 
Secondary objectives: To assess the potential effects of sirolimus on retinal and brain neuroimaging in MSA
 
Exploratory objective: To explore the potential effects of sirolimus on blood biomarkers (exosomal alpha-synuclein particles) in MSA.

Endpoints:	
Primary Endpoint: Change from baseline to 48 weeks (or last available date) in United Multiple System Atrophy Rating Score (UMSARS) total score compared with described progression rates in historical controls. We will assume that patients receiving sirolimus will have a change of 4 points less than those reported in natural history studies (see statistical section).
 
Secondary Endpoints:
 
 1. Change from baseline to 48 weeks (or last available date) in UMSARS-2 subscale score. We will assume that patients receiving sirolimus will have a change of 2 points less than those reported in historical controls. 2. Change from baseline to 48 weeks (or last available date) in UMSARS-1 subscale score. We will assume that patients receiving sirolimus will have a change of 2 points less than those reported in historical controls. 3. Magnetic resonance changes using dedicated algorithms to evaluate rate of change in diffusivity of defined areas of brain from baseline to 48 weeks. 4. Changes in retinal nerve fiber layer using optical coherence tomography from baseline to 48 weeks. 
Exploratory outcome
 
 1. Change in plasma biomarkers (exosomal alpha-synuclein particle concentration) from baseline to 48 months.

Study Population:	A total of 56 patients with multiple system atrophy will be randomized (42 to active agent and 14 to placebo)
Inclusion criteria:	
 1. Participants aged 30-80 years old with a diagnosis of MSA. Patients have to fulfill current consensus criteria (1) for probable MSA of the parkinsonian subtype (MSA-P) or cerebellar subtype (MSA-C). 2. Participants who are less than 4 years from the time of documented MSA diagnosis. 3. Participants who are still able to walk with or without assistance. 4. Participants with an anticipated survival of at least 3 years in the opinion of the investigator. 5. Participants who are willing and able to give informed consent. 6. Montreal Cognitive Assessment (MoCA) > 20. 7. Ability to take oral medication and be willing to adhere to the study drug regimen 8. For females of reproductive potential: use of highly effective contraception during study participation and for an additional 8 weeks after the end of study drug administration 9. For males of reproductive potential: use of condoms or other methods to ensure effective contraception with partner 10. Agreement to adhere to Lifestyle Considerations (see section 5.3) throughout study duration
Exclusion criteria:	
 1. Women of childbearing potential who do not practice an acceptable method of birth control. Acceptable methods of birth control in this study are: surgical sterilization, intrauterine devices, partner's vasectomy, a double-protection method (condom or diaphragm with spermicide), hormonal contraceptive drug (i.e., oral contraceptive, contraceptive patch, long-acting injectable contraceptive) with a required second mode of contraception. 2. Participants with a clinically significant or unstable medical or surgical condition that, in the opinion of the investigator, might preclude safe completion of the study or might affect the results of the study. These include but are not limited to severe, uncontrolled heart failure, recent (<6 months) myocardial infarct, severe, uncontrolled cardiopulmonary disease, severe, uncontrolled hypertension (sustained systolic blood pressure above 200 mmHg in any position), thrombocytopenia (< 50 x 10⁹/L), severe anemia (< 8g/dl), immunocompromised state, liver or kidney disease (creatinine > 1.5 mg/dl or proteinuria > 20 mg/dl), uncontrolled diabetes mellitus (HbA1c >10g%), alcoholism, amyloidosis, uncontrolled hypothyroidism, sympathectomy, unstable peripheral neuropathies, concurrent infections, severe orthopedic problems that compromise mobility and activity of daily living, recent (< 6 month) acute cerebrovascular accidents, neurotoxin or neuroactive drug exposure, parkinsonism due to drugs (including neuroleptics, alpha-methyl dopa, reserpine, metoclopramide). 3. Participants with high LDL cholesterol levels (LDL > 190 mg/dL) and/or high triglycerides levels (> 500 mg/dL). Patients receiving

	
medications for elevated cholesterol or triglycerides are eligible to participate as long as their LDL cholesterol and/or triglyceride levels are below the abovementioned limits.
 
4. Participants with positive interferon-gamma release-assay (QUANTIferon®) indicating latent tuberculosis infection. Participants with a positive Quantiferon® may be enrolled after the patient has been evaluated by an infectious diseases specialist that has cleared the patient for this trial.5. Participants with history of untreated tuberculosis. Participants with a history of treated tuberculosis may be enrolled after an infectious diseases specialist evaluates patient and has cleared the patient for this trial.6. Participants with a history of active, acute or chronic, or latent hepatitis B or hepatitis C.7. Participants with a nasal swab PCR positive for COVID-19. If positive, participant may be re-screened after 1 month. If the second nasal swab PCR is negative for COVID-19, participant may be enrolled.8. Participants with human immunodeficiency virus (HIV) infection, or other congenital or acquired causes of immunosuppression.9. Participants with active malignant neoplasms or history of malignant neoplasm in the last 5 years.10. Movement disorders other than MSA; e.g., Parkinson disease, dementia with Lewy bodies, essential tremor, progressive supranuclear palsy, spinocerebellar ataxia, spastic paraparesis, corticobasal degeneration, or vascular, pharmacological or post-encephalitic parkinsonism.11. Dementia (DSM-V criteria).12. History of electroconvulsive therapy.13. History of deep brain stimulation surgery.14. Patients with contraindication for MRI scanning, including those with MRI-incompatible pacemaker15. History of organ transplant16. Participants who have taken any investigational products within 60 days prior to baseline.17. Treatment with cyclosporine, oral or intravenous corticosteroids, methotrexate, rituximab within 3 months prior to baseline.18. Treatment with inhibitors of CYP3A4 (which may decrease the metabolism of sirolimus and increase sirolimus levels): nifedipine, verapamil, clotrimazole, fluconazole, itraconazole, clarithromycin, erythromycin, troleandomycin, cisapride, metoclopramide, bromocriptine, cimetidine, danazol, HIV-protease inhibitors (e.g., ritonavir, indinavir); grapefruit.19. Treatment with inducers of CYP3A4 (which may increase the metabolism of sirolimus and decrease sirolimus levels): carbamazepine, phenobarbital, phenytoin, rifabutin, rifapentine.20. Inability or unwillingness of subject to give written informed consent.
--	--

Phase:	Phase II
Description of Sites:	Single-center clinical trial performed at the New York University Langone Medical Center
Description of Study Intervention:	Oral sirolimus capsules at a dosage of 2 mg (one 2 mg capsule), 4 mg (two 2 mg capsules) or 6 mg (three 2 mg capsules) taken once a day. Dosage will be adjusted based on determination of sirolimus levels in blood performed throughout the trial and on the frequency of adverse events related to the study drug.
Study Duration:	3 years
Participant Duration:	48 weeks plus a safety follow-up phone call 2 weeks after the end of the trial.

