4 STUDY DESIGN

4.1 OVERALL DESIGN

To determine whether to test sirolimus in a large phase 3 trial, we propose to conduct a clinical trial of sirolimus in MSA using a futility design. A futility design under the null hypothesis assumes that sirolimus will slow the progression of the disease, whereas the alternative hypothesis assumes no benefit of sirolimus. If the null hypothesis is rejected (i.e., futility of sirolimus to slow progression of MSA), major phase 3 studies will be discouraged, whereas non-futility will offer strong support for a phase III trial to detect clinical efficacy.

To test this hypothesis we will perform a single-center, randomized, double blind, placebo-controlled, phase-II, futility trial, chosen as an efficient approach to determine if sirolimus would be worthy of future investigation in larger, more definite trials. This trial was designed to compare the mean value for the primary outcome measure, change in total Unified Multiple System Atrophy Rating Scale (UMSARS) score from baseline to week 48, between the sirolimus arm and a pre-specified fixed value, representing a 4-point reducing in the expected mean decline without treatment; this fixed value was obtained using data from previously completed a large natural history study(39) and the placebo arm of a recently completed clinical trial in MSA (40). The 4-point reduction was based on the recently reported minimally clinically important decline (MICD) in the total UMSARS score of 3.5-points (38).

The null hypothesis is that sirolimus will reduce the mean decline in the total UMSARS score over 12 month by, at least 4-points, compared with the expected (fixed) value obtained from the historical controls. If the null hypothesis is rejected, then the drug would be considered futile for further investigation in MSA. If the null hypothesis is not rejected, sirolimus would be considered for a phase 3 clinical trial.

Thus, the primary goal is to evaluate the effect of sirolimus on progression of MSA, including autonomic, cerebellar and parkinsonian features as measured by the UMSARS, a relevant clinical measure of disease progression. Secondary goals are to determine if there is any effect on neuroimaging (brain MRI) and ophthalmological (retinal OCT) biomarkers of the disease. As exploratory aim we will determine if there are any changes in plasma α Syn exosomes, as surrogate markers of autophagy.

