4.2 SCIENTIFIC RATIONALE FOR STUDY DESIGN

To determine whether to test sirolimus in a large phase 3 trial, we propose to conduct a clinical trial of sirolimus in MSA using a futility design. This approach minimizes the number of subjects and resources required for the study and provides an indication of whether or not to pursue larger and more definite studies. A futility design (60) is highly appropriate for MSA given: a) the low prevalence of the disease; b) the availability of historical controls from recent large studies (8, 39); and c) the availability of sensitive outcome measures. A futility design under the null hypothesis assumes that sirolimus will slow the progression of the disease, whereas the alternative hypothesis assumes no benefit of sirolimus. If the null hypothesis is rejected (i.e., futility of sirolimus to slow progression of MSA), a major phase III study will be discouraged, whereas non-futility will offer strong support for a phase III trial to detect clinical efficacy.

This study will also include a placebo group in 3:1 proportion. Our reason for including a placebo arm is to facilitate blinding to treatment assignment and also to permit a descriptive assessment of the validity of the assumed change in UMSARS over time in the historical control group; it will not be used as a basis of comparison for the active treatment arm.

This placebo-controlled futility design comparing outcome measures to historical controls has been used in other neurodegenerative disorders (61-63).

The study population (n=42 active agent, n=14 placebo) was selected based on power analysis calculation using the known annual progression of the UMSARS total score from published natural history studies (8, 39) and the progression in the placebo group of previous clinical trials of MSA(40), as well as from the minimally clinically significant difference in UMSARS (38) (see statistical section).

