9.2 SAMPLE SIZE DETERMINATION

This study is a randomized, double blind placebo-controlled futility trial in which the primary outcome measure value (UMSARS total score) in a cohort of patients with MSA taking active agent will be compared to a known value from historical controls previously published in the literature. The primary outcome measure was used to calculate the sample size.

The primary statistical analysis will involve a comparison of the mean absolute difference in the active sirolimus group with a pre-specified fixed value, constituting a 4-point reduction in the expected mean increase in the UMSARS total score over 48 weeks without treatment. The expected mean increase in total UMSARS outcomes were obtained from the *U.S. Natural History Study of MSA* (n=96) (39), that reported that the total UMSARS score at 12 months increased a mean of 7.5 (SD: 8.4) absolute points from baseline. Also data from a phase III double-blind placebo-controlled 12-month clinical trial with rifampicin in MSA performed in the U.S. (40) (which was found to be ineffective to slow the progression of the disease) showed that in patients taking placebo (n=50) the total UMSARS score at 12 months increased a mean of 10.8 (SD: 10.7) absolute points from baseline. A weighted analysis of these two populations showed the pooled total UMSARS score at 12-months in patients with MSA in large studies performed in the U.S. had increased a mean of 8.6 (SD: 9.2) points from baseline.

Also, recent studies (38) have determined that the minimally clinically important difference (MCID) in the total UMSARS score is 3.5 points after 48-weeks from baseline.

Taking into consideration this MCID, for this trial, we will assume a promising difference in the UMSARS total score of 4 points between those taking active agent and the historical controls. Specifically, our null hypothesis is that patients receiving sirolimus will have a UMSARS total score progression of only 4.6 points at week 48 higher than baseline, compared to a progression of 8.6 points at week 48 from baseline reported in historical controls from natural history studies and placebo-controlled trials of MSA. Our alternate hypothesis is that sirolimus will be futile to slow the progression of the disease in patients with MSA. The statistical definitions are as follows:

$H_0: \theta_E - \theta_p \leq 4$ where $\theta_p = 8.6$ points increase at week 48 from baseline described in historical controls

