$H_0: \theta_E \leq 4.6$ points increase at week 48 from baseline

$H_1: \theta_E > 4.6$ points increase at week 48 from baseline

Therefore, assuming an alpha of 0.05, and a power of 0.8 (one sided, as patients with MSA have not been reported to improve spontaneously) to detect a progression of 4.6 points (i.e., 8.6 minus 4) in the UMSARS total score after 48-weeks from baseline we will need to enroll 38 patients in the active agent arm. Anticipating a 10% for dropouts rate, we will need to enroll 42 patients in the active agent arm.

This trial will include a placebo group to facilitate blinding in a 3:1 proportion. However, statistical comparisons for the primary and secondary efficacy outcome measures will be performed between the active agent arm and the historical controls. We will therefore enroll 14 patients in the placebo arm.

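### Non-futility is described as strong support for phase III and the alternative as no benefit, but the hypotheses in 9.1 and 9.2 carry neither meaning

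*Combined protocol and SAP*

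**What the plan says.** The Synopsis (1.1) states that "non-futility will offer strong support for a phase III trial to detect clinical efficacy". Section 4.1 says the same, and 4.2 repeats it: "whereas non-futility will offer strong support for a phase III trial to detect clinical efficacy". Section 4.1 adds that "the alternative hypothesis assumes no benefit of sirolimus", and 1.1 and 4.2 describe the alternative in the same terms.

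Later in 4.1 the same result gets a weaker reading: "If the null hypothesis is not rejected, sirolimus would be considered for a phase 3 clinical trial".

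Section 9.2 gives the null hypothesis as "patients receiving sirolimus will have a UMSARS total score progression of only 4.6 points at week 48 higher than baseline". Sections 9.1 and 9.2 write it formally as a mean rise of 4.6 or less, against an alternative of more than 4.6. The untreated benchmark is a pooled historical population that "had increased a mean of 8.6 (SD: 9.2) points from baseline". The design is one-sided, "assuming an alpha of 0.05, and a power of 0.8", with 38 patients needed and 42 enrolled in the active arm. The minimally clinically important difference is given as 3.5 points.

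Section 9.4.2 names a one-sample t-test against 8.6. It declares futility when 8.6 minus the active-arm change is 4 or less. Section 9.4.5 adds an interim look at 24 completers, with stops at an active-arm mean rise of 7 or more (futility) or 4 or less (efficacy).

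**The concern.** In this design the burden of proof lies on showing futility. Failing to reject the null says that the data do not exclude a 4-point slowing. It does not say that slowing has been shown, and it can occur when the estimate is close to the untreated rate. Calling that outcome strong support claims more than the test can deliver, and 4.1 itself uses a weaker phrase for the same outcome.

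The label on the alternative has the mirror-image fault. A mean rise above 4.6 is any slowing of less than 4 points. A drug that slows progression by exactly 3.5 points has a true mean of 8.6 − 3.5 = 5.1, so it belongs to the hypothesis described as no benefit.

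The go/no-go reading is the primary objective. A reader who relies on the Synopsis could take a weak result as a firm basis for a large trial of an immunosuppressant, or take rejection as proof that the drug does nothing.

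**Working it through.** **Inputs (9.2).** Null value 4.6; untreated mean 8.6; SD 9.2; one-sided alpha 0.05; power 0.80; n = 38 evaluable, 42 enrolled.

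**The plan's own figures.**
- Pooled mean: (96 × 7.5 + 50 × 10.8)/146 = 8.63, which agrees with 8.6. The same weighting of the SDs gives (96 × 8.4 + 50 × 10.7)/146 = 9.19, which agrees with 9.2.
- Sample size: n = [9.2 × (1.645 + 0.842)/4]² = 32.7, so 33; the exact t calculation gives 35. The stated 38 is not reproduced. At n = 38 the t-test has power 0.838, so the design is slightly larger than its stated inputs require.

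**Non-futile region under the test in 9.1 and 9.2.** The cutoff for the observed mean is 4.6 + t(0.95, n−1) × 9.2/√n, taking the sample SD as 9.2.
- n = 38: 4.6 + 1.687 × 1.492 = 7.12
- n = 42: 4.6 + 1.683 × 1.420 = 6.99

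The observed slowing at the cutoff is therefore only 1.5 or 1.6 points. The 95% CI half-width is t(0.975, n−1) × 9.2/√n, which is 3.02 or 2.87.
- n = 38: CI at the cutoff 4.1 to 10.1. The interval includes 8.6 once the mean reaches 8.6 − 3.02 = 5.58.
- n = 42: CI at the cutoff 4.1 to 9.9. The interval includes 8.6 once the mean reaches 8.6 − 2.87 = 5.73.

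Means of about 5.6 to 7.1 (n = 38) or 5.7 to 7.0 (n = 42) are thus non-futile with an interval that includes the untreated rate. Lower means exclude it.

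**Chance of a non-futile result.** Without the interim this is the non-central t probability of not rejecting, with non-centrality (true mean − 4.6)/(9.2/√n). With the interim it is simulated (normal data, one million trials per row), assuming 18 of the 24 completers are active (3:1). An efficacy stop counts as a pass, and the P < 0.001 comparisons with placebo are left out.

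| True slowing | True mean | No interim, n = 38 / 42 | With interim stops, n = 38 / 42 |
|---|---|---|---|
| None | 8.6 | 16.2% / 13.0% | 10.6% / 8.9% |
| 2 points | 6.6 | 62.9% / 60.2% | 47% / 46% |
| 3.5 points | 5.1 | 90.6% / 90.3% | 78% / 77% |
| 4 points | 4.6 | 95% / 95% | 85% / 85% |

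**Section 9.4.2 read literally.** Futile if 8.6 − observed mean ≤ 4, that is, if the observed mean is 4.6 or more. The chance of passing is Φ[(4.6 − true mean)/(9.2/√n)].
- Inert drug: Φ(−2.68) = 0.4% (n = 38); Φ(−2.82) = 0.2% (n = 42)
- 3.5-point slowing: Φ(−0.34) = 37%; Φ(−0.35) = 36%
- 4-point slowing: Φ(0) = 50%

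Under this rule the largest upper 95% limit for a non-futile mean is about 4.6 + 3.02 = 7.6 or 4.6 + 2.87 = 7.5, so none reaches 8.6.

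**The case against.** The strongest reply is that the pass rates rest on a decision rule that the analysis section does not state. That stands. Under 9.4.2 as written, an inert drug almost never passes and no non-futile interval includes 8.6 at SD 9.2. A reader might infer that the plan obliges the sponsor to report a result compatible with no effect as strong support. The documents do not support that without qualification, because 9.1 and 9.2 lead to one rule and 9.4.2 to another. The literal rule does not fit the stated alpha of 0.05, since it would wrongly declare a true 4-point drug futile half the time. The test of 4.6 is therefore the more reasonable reading, but the conflict has to be settled.

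Other limits also stand:
- A reader might quote 20% as the inert-drug pass rate. That is the complement of the stated power. At 38 analysed it is 16%, and the interim futility stop lowers it further.
- A type II error of 20% is an openly stated and ordinary choice. The fault lies in the wording of the conclusion.
- Not every non-futile result is compatible with no effect; only the upper part of the region is.
- The 3.5-point case does not mean such a drug would usually be discarded. Without the interim it passes about 90% of the time.
- The plan nowhere says that non-futility demonstrates efficacy. It reserves that for phase III, and 4.2 calls the design an indication of whether to pursue larger studies.

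It is also tempting to demand an upper 95% limit below 8.6 before a result may be called support. That would add an efficacy test against history. A drug with the full 4-point slowing would miss it about 26% (n = 38) or 21% (n = 42) of the time, and 8.6 would be treated as known without error. The documents do not call for it.

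**Conclusion.** The point holds as one of interpretation and internal consistency. Sections 1.1, 4.1 and 4.2 overstate what failing to reject means and mislabel the alternative, and 4.1 states two strengths of conclusion for the same result.

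Under the one-sided 5% t-test of 4.6, an observed slowing of about 1.5 points is enough to pass. An inert drug passes 13 to 16% of the time without the interim and about 9 to 11% with it. A 2-point slowing passes 60 to 63% and about 46 to 47% respectively.

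These figures assume SD 9.2, a true untreated mean of 8.6, 38 or 42 analysed and, for the interim, 18 active patients. Without the interim, the inert-drug rate runs from 8% to 27% as the SD goes from 8.4 to 10.7 (the two historical sources). It is 36 to 40% if the untreated mean here is the 7.5 of the larger source ("increased a mean of 7.5 (SD: 8.4) absolute points from baseline"), and under 1% if it is the 10.8 of the other. All are conditional on resolving 9.4.2. The two wording faults do not depend on these rates.

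**What to change.** - **1.1, 4.1, 4.2:** replace the strong-support sentence with: a 4-point slowing has not been ruled out, and sirolimus would be considered for phase III; this alone is not evidence of efficacy. Describe the alternative as slowing of less than 4 points.
- **9.4.2:** make the decision rule the one-sided 5% t-test of 4.6 that 9.1 and 9.2 define. Report the mean change with its 95% CI against both 4.6 and 8.6, and show the placebo mean beside it descriptively.

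No added patients, visits or data are needed. The cost is a protocol amendment, and the claim attached to a non-futile result becomes less favourable.
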